3.2 Primary Study Endpoints

The primary endpoint will be the PCWP at 20 Watts exercise after study drug relative to the PCWP at 20 Watts exercise in the initial assessment prior to study drug.

3.3 Secondary Study Endpoints

Secondary exploratory endpoints will be changes in resting PCWP after study drug as well as rest and exercise changes in right atrial pressure, pulmonary artery pressure, pulmonary vascular resistance and compliance, coronary sinus saturation, systemic BP, heart rate, cardiac output, A- V O₂ content difference during exercise, VO₂, Ve/VCO₂ slope and Borg effort/dyspnea scores. Increase in cGMP in response to MPO inhibition along with changes in other biomarkers and MPO described above will also be assessed.

3.4 Primary Safety Endpoints

Safety and tolerability will be measured by the incidence of SAEs, AEs and clinical changes in ECG, vital signs and clinical laboratory evaluations.

A maculopapular skin rash can occur which will be monitored. The characteristics of the rash will be documented. Photos including a body overview photo plus a more detailed photo of a representative affected skin area will be taken, if rash occurs. Dermatologic evaluation with biopsy if deemed necessary will be obtained for significant rashes.

3.5 Identification of Source Data

The following source data will be directly recorded on the Case Report Form (CRF):

- Echo findings at baseline, during cath
- EndoPAT
- History and Physical Exam
- Hemodynamic data from all study phases
- Clinical data and Demographics

The following source data will not be directly collected in the Case Report Form (CRF), but will be captured in supportive documentation (study source documents, EMR):

- Laboratory results and clinical interpretation of the values.
- ECG records and clinical significance of observations (when applicable)

4 Subject Selection Enrollment and Withdrawal

4.1 Inclusion Criteria

1. Males and females of non-childbearing potential confirmed at screening by fulfilling one of the following criteria:
 - Postmenopausal defined as amenorrhoea for at least 12 months or more following cessation of all exogenous hormonal treatments and follicle-stimulating hormone (FSH) levels in the postmenopausal range
 - Documentation of irreversible surgical sterilisation by hysterectomy, bilateral oophorectomy or bilateral salpingectomy but not tubal ligation
2. Age \geq 30 years
3. Symptoms of dyspnea (II-IV) at the time of screening
4. EF \geq 50% as determined on imaging study within 12 months of enrollment
5. Catheterization documented elevated filling pressures at rest (PCWP \geq 15) or with exercise (PCWP \geq 25)

4.2 Exclusion Criteria

1. Use of nitrates, phosphodiesterase 5 inhibitors or other NO-providing therapy in the past 24 hours of screening
2. Significant valvular disease ($>$ moderate left-sided regurgitation, $>$ mild stenosis)
3. Requirement of intravenous heparin at the start of case
4. Severe pulmonary parenchymal disease
5. Acute coronary syndrome or coronary disease requiring revascularization in the judgement of investigators
6. Resting systolic blood pressure $<$ 100 mmHg
7. Constrictive pericarditis

8. Infiltrative, restrictive, or hypertrophic obstructive cardiomyopathies
9. Previous anaphylaxis to any drug
10. Pregnancy or breastfeeding mothers
11. High Output heart failure
12. Active thyroid disease
13. Treatment with a new chemical entity (defined as a compound which has not been approved for marketing) within the preceding 3 months
14. Patients with any prior allergy to propylthiouracil

4.3 Subject Recruitment, Enrollment and Screening

Eligible patients will be identified from screening of the patients listed for exercise right heart catheterization as well as patients with known HFrEF at the Mayo Clinic in Rochester, Minnesota.

4.4 Early Withdrawal of Subjects

4.4.1 When and How to Withdraw Subjects

Development of any condition that requires study withdrawal related to safety, disease progression, subject decision or failure to adhere to protocol requirements could qualify as reason to withdraw from the study.

4.4.2 Data Collection and Follow-up for Withdrawn Subjects

Subjects withdrawing from the study will be contacted 2 weeks following study drug administration to ensure that there have been no adverse events. Participants that withdraw may be replaced to allow for achievement of target enrollment.

4.5 Pregnancy

All pregnancies and outcomes of pregnancy should be reported to the sponsor and AstraZeneca.

4.5.1 Maternal Exposure

Pregnancy itself is not regarded as an AE unless there is a suspicion that the IP under study may have interfered with the effectiveness of a contraceptive medication. Congenital abnormalities/birth defects and spontaneous miscarriages should be reported and handled as SAEs. Elective abortions without complications should not be handled as AEs.

The outcome of all pregnancies (including spontaneous miscarriage, elective termination, and ectopic pregnancy) will be documented.

If any pregnancy occurs in the course of the study, then the Investigator or other site personnel informs the sponsor's representatives within 1 day of when he/she became aware of it.

4.6 Reproductive Restrictions

It is important that women of childbearing potential, who are the partners of male subjects, do not become pregnant during the study and for a total period of 3 months after subjects have taken the last dose of IMP.

Non-sterilized males who are sexually active with a female partner of childbearing potential must use condom and spermicide from Day 1 through and for a total period of 3 months after subjects have taken the last dose of IMP. Because male condom and spermicide is not a highly effective contraception method it is strongly recommended that female partners of male study subjects also use a highly effective method of contraception throughout this period.

Highly effective contraception is defined as having a low failure rate, i.e., less than 1% per year when used consistently and correctly. Highly effective contraception forms of birth control include:

Tubal occlusion

- Copper T intrauterine device
- Levonorgestrel-releasing intrauterine system (e.g., Mirena®)
- Medroxyprogesterone injections (e.g., Depo-Provera®)
- Etonogestrel implants (e.g., Implanon®, Norplant®)
- Combined pills
- Norelgestromin/ethinyl estradiol transdermal system (e.g., Ortho Evra®)
- Intravaginal device (e.g., NuvaRing®)
- Cerazette® pill

Male subjects who have been sterilized are required to use 1 barrier method of contraception (condom).

Sperm Donation

Male subjects should not donate sperm for the duration of the study and for at least 3 months after the last day of IMP administration.

Pregnancy

Subjects will be instructed that if their partner becomes pregnant during the study this should be reported to the Investigator. The Investigator should also be notified of pregnancy occurring during the study but confirmed after completion of the study. In the event that a subject's partner is subsequently found to be pregnant after the subject is included in the study, then consent will be sought from the partner and if granted any pregnancy will be followed and the status of mother and/or child will be reported to the sponsor after delivery.

A pregnancy notification form and follow-up will be completed.

5 Study Drug

5.1 Description

The IMP (Investigational Medicinal Product) is a white film-coated tablet containing 5 mg of AZD4831. A matched placebo (**PTM AZD4831 film-coated tablet 5 mg**) is also presented. The IMP will be manufactured by AstraZeneca in accordance with Good Manufacturing Practice (GMP).

5.2 Treatment Regimen

A single administration of MPO inhibitor at a dose of 30 mg or matched placebo, will be given orally following baseline exercise right heart catheterization, if patients meet the above eligibility criteria.

5.3 Method for Assigning Subjects to Treatment Groups

Patients will be randomized 1:1 in a blinded fashion to AZD4831 or placebo with blinding and randomization performed by the Mayo Clinic Research Pharmacy.

5.4 Preparation and Administration of Study Drug

The IMP will be provided in bulk from AstraZeneca, to be packed into study specific containers with study specific labels by the pharmacy, according to the bottling instruction provided by AstraZeneca.

The **AZD4831 film-coated tablet 5 mg** and **PTM AZD4831 film-coated tablet 5 mg** will be supplied in induction-sealed high-density polyethylene bottles with silica desiccant.

5.5 Subject Compliance Monitoring

This will be a single dose, directly observed dosing study so formal checks for long term compliance are not necessary

5.6 Prior and Concomitant Therapy

Participants' chronic medications will not be changed for the purposes of this study. They will continue taking their home medications as prescribed up until the morning of the procedure. Data for baseline medication usage will be obtained.

5.7 Packaging

AZD4831 film-coated tablet 5 mg and PTM AZD4831 film-coated tablet 5 mg will be delivered in bulk from AstraZeneca. Empty bottles, caps and desiccant will be delivered separately. Each bottle should be filled with 35 tablets, with 2 desiccant unit added, and be capped and labelled appropriately, including information of expiry date in accordance with bulk information.

5.8 Masking/Blinding of Study

Only research pharmacy staff will be aware of randomization scheme and all study personnel and subjects will remain blinded to the identity of study drug.

5.9 Receiving, Storage, Dispensing and Return

5.9.1 Receipt of Drug Supplies

Upon receipt of the study treatment supplies, an inventory must be performed and a drug receipt log filled out by the person accepting the shipment. It is important that the designated study staff counts and verifies that the shipment contains all the items noted in the shipping invoice. Any discrepancies, damaged or unusable study drug in a given shipment (active drug or comparator) will be documented in the study files. The sponsor-investigator must be notified immediately of any discrepancies, damaged or unusable products that are received.

5.9.2 Storage

The IMP will be stored in a secure facility under appropriate storage conditions. The IMP should be stored in room temperature (<30°C) protected from light prior to use. Details of storage conditions will be provided on the label of the IMP.

5.9.3 Dispensing of Study Drug

Regular study drug reconciliation will be performed to document drug assigned, drug dispensed, drug returns, and drug remaining. This reconciliation will be logged on the drug reconciliation form, and signed and dated by the study team.

5.9.4 Return or Destruction of Study Drug

At the completion of the study, there will be a final reconciliation of drug shipped, drug dispensed, drug returns, and drug remaining. This reconciliation will be logged on the drug reconciliation form, signed and dated. Any discrepancies noted will be documented and investigated, prior to return or destruction of unused study drug. Drug destroyed on site will be documented in the study files.

6 Study Procedures

6.1 Visit 1

At Visit 1, subjects will provide written informed consent. Medications will be documented. Safety blood tests (complete blood count, creatinine, blood urea nitrogen, sodium, potassium, TSH and T4, aspartate aminotransferase, alanine aminotransferase, total, direct and indirect bilirubin) hs c-RP, NTproBNP, assessment of endothelial function, radial tonometry for pulse wave analysis, and comprehensive echocardiography will be performed before catheterization.

Invasive right heart catheterization with simultaneous limited echocardiography and expired gas analysis will then be performed at rest and during 20 watts of ergometer exercise as per standard practice for the evaluation of unexplained dyspnea (5 minute exercise duration). Subjects will be given study drug (AZD4831 or matching placebo) orally followed by 30 minutes waiting period in the cath lab to facilitate therapeutic concentration.

Patients will then repeat resting and exercise invasive catheterization at 20 W in exactly the same fashion as prior to study drug. Blood samples will be collected before and after study drug to measure biomarkers of oxidative stress, NO activity and PK.

Following completion of both rest-exercise runs, participants will receive a bolus of intravenous heparin (70 U/kg) to displace tissue MPO. By comparing MPO concentrations and activity prior to study drug, following study drug and then following heparin, we will be able to relate MPO activity to the pharmacodynamic effects of study drug on central hemodynamics.

Subjects will be transferred to the catheterization lab recovery area as per standard clinical practice, where intravascular sheaths will be removed and

hemostasis obtained. Participants will be monitored according to standard practice guidelines following exercise right heart catheterization procedures and discharged on the same day. A repeat EndoPAT test will be performed while the patients are in the recovery area.

[figure not shown]
6.2 Visit 2

Visit 2 will be scheduled on day 9-14 after dosing and will be a virtual, NFTF (non-face to face) visit, performed through use of Zoom, similar to other NFTF visits performed clinically at Mayo Clinic. The focus at the virtual NFTF visit will be to assess for any symptoms or adverse events and to perform a full skin examination by video, given the potential for maculopapular rash. If a clinically significant rash is identified dermatologic consultation will be obtained with biopsy if deemed appropriate by the consulting dermatologist. Patients will be instructed to report back immediately if they develop a rash prior to the follow up visit.

Study Assessments (Figure 3):

Right heart catheterization will be performed using high fidelity micromanometers at rest and during supine exercise with simultaneous expired gas analysis (MedGraphics, St. Paul, MN, USA). A 9 Fr Internal jugular catheter for continuous right atrial pressure and to allow introduction of a balloon tipped fluid filled catheter will be placed in the right internal jugular vein. A high Fidelity micromanometer wire will be placed in the balloon wedge catheter to enable accurate pressure recording with exercise. A 4 Fr radial arterial cannula will also be placed for continuous arterial pressure measurement and arterial saturation with exercise (all standard care). The coronary sinus is cannulated at select times to measure myocardial biomarkers and indicators of metabolism. Figure 3 shows the assessments performed in the protocol. The protocol is rest—passive leg elevation—20 Watts exercise for 5 minutes. Hemodynamics, venous, arterial and coronary sinus blood samples, arterial and mixed venous blood gas and expired gas

Figure 3: Assessments During Testing

data are acquired at rest, and during exercise. Detailed list of assessments and timing is found in Appendix I.

Exercise is not performed to exhaustion, but we have previously shown that 80-90% of the increases in cardiac filling pressures that will occur with exercise occur at 20W workload in HFrEF, and the requirement to perform 2 studies in the same day dictates that this lower workload is used uniformly in both tests. Of note, this workload is close to maximal in most patients with HFrEF, and most relevant to the workload of activities of daily living with affected patients. Perceived symptoms of dyspnea and fatigue will be quantified using the Borg dyspnea and effort scores during exercise.

After the initial exercise study, the oral study drug (30 mg AZD4831 or placebo) will be provided. After a 30 minute waiting period for absorption and therapeutic concentration, subjects will repeat resting and exercise hemodynamics with expired gas data acquired exactly as in the initial run including venous, arterial and coronary sinus sampling at rest and exercise.

Heparin will not be used during the studies due to its known effect on liberating vascular MPO and increasing NO bioavailability.³⁸ At the conclusion of the study, a single bolus of heparin will be administered (70 units/kg) to evaluate vascular MPO levels and activity present in subjects. This will provide a more sensitive measure of tissue MPO activity after drug inhibition to correlate with hemodynamics. Both MPO level and activity will be measured, to allow quantification of specific activity. The blood sample collection for MPO assessment will be done at rest and following exercise, both before and after study drug. In addition following the exercise portion of the study it will be measured before and after heparin administration. Protamine will be given following final laboratory assessments prior to sheath removal to minimize risk of bleeding.

Comprehensive echocardiography will be performed before catheterization for descriptive purposes (appendix II).

[figure not shown]
Aortic pulse wave analysis will be determined from invasive radial artery pressure waveforms obtained during the cardiac catheterization procedure.

Focused echocardiography will be done simultaneously with cardiac catheterization focusing on cardiac volumes and measures of biventricular systolic and diastolic function using strain and Tissue Doppler (appendix III). Measurements will be repeated at rest and during exercise before and after the study drug.

Blood samples will be collected during catheterization. Up to 150 cc of blood will be taken to measure arterial and venous blood gases, saturations, and cyclic guanosine monophosphate (cGMP) levels at rest and exercise. Baseline blood samples will be obtained for MPO activity (MPO concentration and activity, Arg/ADMA/SDMA) level and biomarkers of inflammation/oxidative stress (cRP, troponin I, GDF-15, NO metabolites), fibrosis/remodeling (C-

telopeptide Cl, sST2, MMP, galactin 3, Pro-collagen III N-terminal peptide) and neurohormonal activation (NT proBNP).

Purine metabolites (hypoxanthine, xanthine, urate and allantoin) will also be quantified at these time points as this may provide important information regarding the mechanisms behind MPO-driven urate reduction. High sensitivity troponin will be assessed as an indicator of myocardial stress. The metabolites and troponin levels will be quantified in samples drawn from the radial artery, superior vena cava, the coronary sinus and from the main pulmonary artery to determine impact of AZD4831 on the different vascular beds. All metabolites should increase in the circulation at exercise. If MPO is a “vasomotor controller, as is believed, then pretreatment with AZD4831 should decrease the concentration of all metabolites. If MPO inhibition only affects the oxidation of hypoxanthine and xanthine, the concentration of these metabolites should be unaffected/increased and urate and allantoin decreased. If AZD4831 unloads the heart, this may reduce troponin levels in the circulation, particularly in the coronary sinus samples. A detailed list of blood sample testing is included below.

a = Safety blood tests + NT-proBNP. Analyzed at Mayo (hematology, liver, kidney, thyroid status).
b = HF-related biomarkers analysed by TATAA Biocenter (possibly a combination of 3 ProSeek panels from OLINK). 5 mL blood. Plasma divided into 0.5 mL aliquots
c = Biomarkers related to MPO biology analysed by AZ (purine metabolites, MPO concentration and activity, Arg/ADMA/SDMA).
d = Blood gases
e = cGMP
f = PK sampling. Exposure analyzed by AZ. 2 mL blood/timepoint.

BL, baseline; EX, exercise at 20W; PA, pulmonary artery; Art, radial artery; Cor Sinus, coronary sinus

Endothelial function testing will be assessed by pulse wave analysis using the Endo PAT (Peripheral Arterial Tone) ⁴⁰ system before study drug. Indirect serological surrogates of endothelial function including plasma cGMP and NO metabolites will also be assessed before and after study drug. The Endo PAT will be performed for baseline values before catheterization in preparation room and for follow-up values in the recovery area following the procedure, but prior to discharge.

7 Statistical Plan

7.1 Sample Size Determination

No data is available on the effect of an oral MPO inhibitor on exercise PCWP in humans. Based on our previously published data on IV sodium nitrite, the decrease in exercise PCWP was 2 ± 5 with placebo and 11 ± 5 with sodium nitrite ³⁵. To detect a decrease in PCWP magnitude of this magnitude or greater compared to placebo with 80% power at an $\alpha=0.05$, only 6 subjects would be required in each group.

However, since we expect the magnitude of hemodynamic effect of an oral MPO inhibitor to be at least 25% less than that of IV sodium nitrite (which would still be a meaningful decrease in PCWP); we will enroll 18 patients in each arm for a total of 36 patients. This will allow for 80% power to detect a reduction in exercise PCWP of 5.3 mmHg or greater, which would be considered to be clinically significant.

7.2 Primary Outcome Analysis

Primary Statistical Hypotheses:

Ha: Exercise PCWP values at 20 Watt workload after study drug relative to corresponding values at 20 Watts workload prior to study drug will be lower after study drug administration compared to placebo

Analysis Summary:

The effect of AZD4831 on the primary endpoint of exercise PCWP will be assessed by analysis of covariance, using the initial exercise PCWP measured before study drug infusion and exercise PCWP following study drug as the covariates. Statistical testing for the primary analysis will be two-sided at the alpha=0.05 level of significance. Other details of the statistical approach will be included in the Statistical Analysis Plan (SAP).

8 Safety and Adverse Events

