Study Product, Dose, Route, Regimen	Oral administration of MPO inhibitor (AZD4831 tablets 5 mg and matching AZD4831 Placebo tablets) at a dose of 30 mg during catheterization
Duration of Administration	Single administration
Reference therapy	Placebo
Statistical Methodology	The principal comparisons will be exercise hemodynamic parameters at 20 Watt workload after study drug relative to corresponding values at 20 Watts workload prior to study drug. Primary hypotheses will be tested using analysis of covariance.

Introduction

Heart failure (HF) with preserved ejection fraction (HFpEF) has become the most common cause of HF. Morbidity and mortality are high and there is no proven effective pharmacological treatment, making this a huge unmet public health need. Recently, abnormalities in Nitric Oxide (NO) signaling and Reactive Oxygen Species (ROS) generation have been implicated as a unifying mechanism by which aging and associated systemic comorbidities drive the myocardial and peripheral limitations that constrain exercise capacity in HFpEF. Myeloperoxidase (MPO) is a leukocyte enzyme that plays a key role in host defense but has also recently been implicated in the pathophysiology of incident cardiovascular diseases, including HF. MPO plays an important role in the regulation of vascular tone and arterial conduit function, since vascular MPO activity results in NO scavenging. Because loss of NO activity is heavily implicated in the pathogenesis of HFpEF, MPO inhibition may represent a novel therapeutic approach to target the NO imbalance and vascular dysfunction that exists in HFpEF.

Accordingly, **our guiding hypothesis** is that an oral MPO inhibitor (AZD4831) will improve cardiac hemodynamics at rest and during exercise in relation to enhanced NO bioavailability. This Proof of Principle study will assess the effect of a single dose of an oral acute MPO inhibitor on resting and exercise hemodynamics in patients with HFpEF referred to the catheterization lab. In addition, we will evaluate NO bioavailability, cyclic Guanosine Monophosphate (cGMP) response and forearm flow mediated vasodilation as surrogate markers for improving endothelial function with MPO inhibition.

This document is a protocol for a human research study. This study will be carried out in accordance with applicable United States government regulations and Mayo Clinic research policies and procedures.

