- 9) The primary analysis will compare resting and exercise hemodynamic response after AZD4831 or placebo relative to the initial assessment 2-way ANCOVA (using the baseline value as the covariate).
- 10) A follow up, non-face-to-face videoconference visit will be scheduled between days 9-14 after dosing. History and visual physical exam (including full skin exam) will be repeated. Patients will be instructed to report back immediately if they develop a rash prior to the follow up visit.

Figure 2: Study Flow Diagram

Innovation:

- The use of exercise hemodynamics to measure an intervention's effect is highly novel and clinically meaningful because exercise is the time where symptoms develop and hemodynamics are most perturbed in response to heightened physiological demand. Very few centers in the world could carry out this study.
- The hypothesis that NO availability is limited in part by increased vascular MPO activity is novel and has not been tested in HFrEF.
- No previous therapy in HFrEF has directly targeted the vascular processes that result in both decreased NO and increased ROS that are believed to be the underlying driver of global cardiac and peripheral reserve limitations in HFrEF.
- Myocardial efficiency, assessed by myocardial O₂ consumption (using coronary sinus sampling) in relation to myocardial performance, is a highly sensitive method of detecting drug effect on myocardial function.

Significance:

- HFrEF afflicts millions worldwide, and with the aging population the prevalence is growing by 1% per year. This makes identification of effective treatments a major unmet public health need with the potential to change clinical practice.
- MPO inhibition has the potential to uniquely target the underlying hyperactive oxidative stress and inflammation that is believed to represent a common pathway driving the phenotypically diverse HFrEF syndrome.
- In addition, augmentation of NO bioavailability by decreasing its oxidation through MPO inhibition has the potential to improve exercise capacity. This is a clinically relevant end point in this population defined by exercise intolerance.
- Identification of a beneficial effect of MPO inhibition on hemodynamics would provide critical preliminary data to support a larger scale clinical trial in HFrEF focused on surrogate markers of HF severity, exercise tolerance or cardiac remodeling.

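### Section 7.2 lists the post-drug exercise PCWP, which is the outcome, as a covariate in the primary ANCOVA; as written the model cannot test treatment, and it conflicts with Section 3.1 step 9

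*Combined protocol and SAP*

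**What the plan says.** Four places in the protocol bear on the primary model.

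- **Section 3.2** defines the endpoint: "The primary endpoint will be the PCWP at 20 Watts exercise after study drug", compared with the same measurement made before dosing.
- **Section 7.2** names the method, "The effect of AZD4831 on the primary endpoint of exercise PCWP will be assessed by analysis of covariance", and then the covariates, "using the initial exercise PCWP measured before study drug infusion and exercise PCWP following study drug as the covariates". The test is two-sided at 0.05. The section closes with "Other details of the statistical approach will be included in the Statistical Analysis Plan (SAP").
- **Section 3.1, step 9** describes the primary analysis as a "2-way ANCOVA (using the baseline value as the covariate"). That is one covariate.
- **The Study Summary** (Statistical Methodology) says "Primary hypotheses will be tested using analysis of covariance" and names no covariate.

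Section 7.1 sizes the trial in absolute mmHg, with 18 patients per arm and "80% power to detect a reduction in exercise PCWP of 5.3 mmHg or greater".

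**The concern.** The second covariate in Section 7.2 is not a baseline characteristic. It is the measurement that the treatment is meant to change. If the outcome is the post-drug value, the model regresses that value on itself. If the outcome is the change, the model regresses it on its own two components. In either case nothing is left for the treatment term to explain.

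Section 7.2 is where an analyst or reader looks for the pre-specified primary model. If that model cannot be run, someone must choose another. In a 36-patient trial with one primary test, that choice should be on record before unblinding. Step 9 offers a usable covariate, but it sits in a brief synopsis, and nothing gives it precedence over Section 7.2.

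**Working it through.** **Inputs.** From the protocol: 18 per arm, 1:1 (Sections 7.1, 5.3); two-sided alpha 0.05 (Section 7.2); SD of the change 5 mmHg in each arm, and falls of 2 mmHg on placebo and 11 mmHg on sodium nitrite, a difference of 11 − 2 = 9 mmHg (Section 7.1); planned difference 5.3 mmHg (Section 7.1). The protocol gives no mean or SD for pre-drug exercise PCWP, so these are assumed where a simulation needs them.

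**The plan's own figures.** A two-sample t-test with difference 9 and SD 5 needs 5.98, so 6 per group, which matches Section 7.1. For 5.3 mmHg with SD 5 and 18 per arm, power is 87.1%, not 80%. At 80% power, 18 per arm detects 4.8 mmHg; 15 per arm detects 5.3 mmHg. The stated power is therefore conservative. That is a separate matter and does not affect this point.

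**The Section 7.2 model, read literally.** The regressors are intercept, arm, pre and post, leaving 36 − 4 = 32 residual degrees of freedom.

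- Outcome = post-drug value: post = 0·arm + 0·pre + 1·post.
- Outcome = absolute change: post − pre = 0·arm − 1·pre + 1·post.

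Both are exact identities. The residual sum of squares is 0, the arm coefficient is 0, and its test statistic is 0/0, whatever the drug does. A simulation with 18 per arm and 5,000 trials at each true difference of 0, 5.3 and 9 mmHg agrees: the largest absolute arm coefficient was 7.3 × 10⁻¹⁴ mmHg and the largest residual sum of squares 2.2 × 10⁻²³, which is rounding error.

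**If the endpoint is read as a ratio.** Section 3.2 does not state the scale. With post/pre as outcome the fit is no longer exact, but treatment is still not tested. In 2,000 simulated trials with a true effect of 5.3 mmHg (assumed pre-drug mean 32, SD 5), the literal model rejected in 2.0%, against 84% with the pre-drug value as the only covariate.

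**The model with the pre-drug covariate only.** The regressors are intercept, arm and pre, leaving 36 − 3 = 33 residual degrees of freedom. The approximate 95% confidence interval half-width is

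t(0.975, 33) × 5 × √(1 − R²) × √(2/18),

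where R² is the share of the variance of the change explained by baseline.

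| R² | Half-width (mmHg) |
|---|---|
| 0 | 3.39 |
| 0.25 (assumed) | 2.94 |

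In 2,000 simulated trials (assumed pre-drug mean 32, SD 7; SD of change 5) this model rejected in 5.2% with no effect and in 86% with a 5.3 mmHg effect, with a mean estimate of −5.3 mmHg.

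**Post-drug value or change as outcome.** If post = a + b·arm + c·pre, then post − pre = a + b·arm + (c − 1)·pre. Only the coefficient of the pre-drug value differs. The treatment estimate, its standard error and its p-value are the same.

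**The case against.** The strongest reply is that this is a drafting slip whose intent can be recovered. Step 9 names the baseline value alone, and the alternative hypothesis in Section 7.2 describes a between-arm comparison of post-drug relative to pre-drug PCWP. The same sentence in Section 7.2 refers to an infusion although the study drug is an oral tablet (Sections 5.1 and 5.2), which also suggests loose wording. No analyst would report a fit with zero residuals, so no bias, inflated error rate or loss of power would reach a published result. This stands as an argument about weight, and it limits the practical harm. It does not make the sentence correct or settle which statement governs.

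A second reply is that a separate SAP may give the right model. That cannot be excluded, since no separate SAP text is in the supplied document. But Section 7.2 leaves only further details to the SAP and states the covariates as already decided, so the protocol would need correcting in any case.

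A third reply is that step 9 has faults of its own: it calls the ANCOVA two-way without naming a second factor, and it describes the primary analysis as covering resting as well as exercise hemodynamics. That is true, but it is a separate matter and does not weaken the correction to Section 7.2.

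**Conclusion.** The concern holds. Read literally, the primary model in Section 7.2 returns a treatment effect of 0 mmHg with no residual variance for any true effect, and its covariate list conflicts with Section 3.1 step 9. For the post-drug value or the absolute change as outcome this is algebra and needs no assumption. For a ratio outcome, the failure to test treatment rests on a simulation with an assumed baseline distribution. The half-widths of 3.4 and 2.9 mmHg describe the precision of the corrected model, not the size of the fault; they rest on the Section 7.1 SD of 5 mmHg, and the second also on an assumed R² of 25%.

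The practical cost is an unusable and contradictory statement of the primary analysis, not a likely wrong result. It should be fixed before unblinding.

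**What to change.** Rewrite the covariate sentence in Section 7.2 to state:

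- dependent variable: post-drug PCWP at 20 W (or, equivalently, its absolute change from the pre-drug value);
- factor: treatment arm;
- only covariate: pre-drug PCWP at 20 W;
- reported result: adjusted mean difference between arms with 95% confidence interval, two-sided alpha 0.05.

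This agrees with step 9 on the covariate, and any separate SAP should carry the same model. The cost is a wording change to one sentence, with no added patients, visits or measurements. The loose wording of step 9 could be tidied in the same amendment, but the correction does not depend on it.
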